8 STUDY PROCEDURES

8.1 STUDY PROCEDURES/EVALUATIONS

The CHE's will deliver evidence-based educational material (i.e., toolkits) via one-on-one sessions to a total sample of 400 participants. Participants will be given the option to have the education presented over the phone or via zoom. The CHE will use educational materials on HPV, HPV-related cancers, and the HPV vaccine and to motivate participants to initiate and complete the HPV vaccine. The CHE will administer post education surveys to participants. Educational material will be presented separately in English or in Spanish. Participants will be invited to participate in their preferred language. Name, telephone number, address will also be collected in order to administer the follow-up calls. Participants will be given a \$25.00 gift card for completing the post education survey.

Those that choose to participate in the evaluation process of the education materials will complete the informed consent process and complete the immediate post education survey. Those that indicate not being vaccinated on the immediate post education survey will be contacted to participate in the 3-month follow up survey. If participants missed a scheduled vaccine dose or indicate they have not been vaccinated at 3 months, they will be contacted again at 6 months for follow up.

Additionally, the PN will refer those that are interested in receiving the HPV vaccine to the PN. During the delivery of the PN intervention, the PN will track participants that a) receive a 1st dose, 2nd dose, or 3rd dose of the HPV vaccine; and connections to care by recording the number of services provided including (b) patients connected to health insurance, discount or no-cost HPV vaccine programs; or (c) other services to facilitate HPV vaccine dose completion (e.g., language translation, appointment scheduling assistance, transportation services, childcare).

We will track HPV vaccine doses at the patient-level and rates at DHHA clinics to the access the system-level impact of the interventions on increases overall HPV vaccination rates for adolescents (9-17 years old) and young adults (18-26) in the respective DHHA clinics. Our goal is to conduct the educational sessions and the post education survey in person. However, current circumstances as a result of the COVID-19 outbreak require we execute our educational sessions remotely. We will send educational material to be watched via REDCap links or present the materials over Zoom or over the phone. Secured REDCap links will be used to obtain the post education survey. We will also use REDCap to obtain any PHI needed to for follow up.

Post education surveys will be physically mailed, without any PHI, to the NCI after we have uploaded and stored the surveys in REDCap.

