- 3) *To assess clinic-level impact, we will obtain clinic vaccination reports track the number of patients at each clinic who received: (a) 1st dose, 2nd dose, or 3rd dose of the HPV vaccine at baseline; and record quarterly: (b) 1st dose, 2nd dose, or 3rd dose of the vaccine broken by age for adolescents (9 to 17 years old) and young adults (18-26 years old).*

Population:

- ***Sample size***

- *Maximum number of participants that can be enrolled is 1000*
- *Minimum number of participants to be enrolled 400 (number of participants needed for analyses)*

Phase: N/A

Participating Sites: Denver Health and Hospital Authority

Description of Study

Intervention: Education and Patient Navigation

[figure not shown]
Study Duration: 36 months

Participant Duration:

Duration will vary for each participant and will be determined by vaccination status. Participants will be contacted to complete a post-education at baseline using the NCI survey. We will only administer the survey pages 1-3.

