4 STUDY DESIGN

4.1 OVERALL DESIGN

We will use a one-group post-test design to assess the effects of the intervention on the primary outcomes. The educational intervention will be delivered to 400 participants by a trained CHE who will deliver the educational materials to eligible DHHA patients. The CHE will administer the post-education survey at baseline to participants. Additionally, we will use a one-group post-test design to assess the impact of the intervention on the secondary outcomes. At the patient-level, we will track participants that receive (a) 1st dose, 2nd dose, or 3rd dose of the HPV vaccine; and the number of referrals to care by recording the number of patients received (b) referrals to health insurance, discount, or no-cost HPV vaccine programs; or (c) to other services to facilitate HPV vaccine dose completion. To assess clinic-level impact, we will track each clinic's HPV vaccine rates for adolescents (9-17 years old) and young adults (18-26) and compare rates from before we start the intervention and then quarterly thereafter we have introduced the intervention to each respective Denver Health clinic.

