5 STUDY POPULATION

5.1 INCLUSION CRITERIA

In order to be eligible to participate in this study, an individual must meet all of the following criteria:

Denver Health Patients:

1. Be a Denver Health patient* 18-26 years old, who has not started or completed the HPV vaccine series (Vaccine completion for this age group is 3 doses).
2. Be a parent of a Denver Health adolescent patient* aged 9-17 years old (), who has not started or completed the HPV vaccine series. (Vaccine completion is 2 doses for 9-14-year-old, and 3 doses for 14-17-year-old)
3. English and/or Spanish Speaking
4. Stated willingness to comply with all study procedures and be available for the duration of the study.

* Denver Health patients will be identified from one of the following clinics: Denver Health Clinics Eastside Adult Clinic, Eastside Women's Care Clinic, Westside Adult Clinic, Westside Women's Care Clinic, Pavilion C: Women's Care Clinic, La Casa-Quigg Newton Family Health Center, Lowry Family Health Center, Montbello Family Health Center, Westwood Family Health Center, Parkhill Family Health Center, Webb Center For Primary Care, Pena Southwest Clinic

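### With one-to-one delivery to 400 participants from 12 clinics, a single clinic's overall vaccination rate is very unlikely to show the effect, and uncontrolled clinic or system rate changes should not be read as impact

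*Protocol*

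**What the plan says.** The synopsis (1.1) lists clinic- and system-level impact of navigation under the secondary objectives. The matching endpoints appear there, and in the table of section 3, as tertiary/exploratory.

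The measure is the whole clinic. Section 8.1: "We will track HPV vaccine doses at the patient-level and rates at DHHA clinics to the access the system-level impact of the interventions". Section 4.1 says the sponsor will "compare rates from before we start the intervention and then quarterly thereafter", clinic by clinic. The synopsis adds that the quarterly clinic counts are "broken by age for adolescents (9 to 17 years old) and young adults (18-26 years old". Section 4.2 compares the system's rates with state rates. The design in 4.1 is one-group, with no control clinics.

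The intervention acts on individuals. Section 8.1 delivers education "via one-on-one sessions to a total sample of 400 participants", and 6.2 and 8.2.3 offer navigation to those participants who still need doses. Section 5.1 states that "Denver Health patients will be identified from one of the following clinics", and 12 names follow. The synopsis gives "Minimum number of participants to be enrolled 400 (number of participants needed for analyses" and "Maximum number of participants that can be enrolled is 1000". Section 4.3 ends the study once 400 are recruited, so 400 is the operative figure and 1000 a ceiling.

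**The concern.** The unit of delivery is a person and the unit of measurement is a clinic. A clinic's rate averages over all its eligible patients, most of whom, unless the clinic is small, are outside the study. Two errors follow if the clinic rate is read as the intervention's impact. A real benefit among participants can be lost in the clinic figure, and a swing among other patients can be credited to the intervention.

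This is distinct from the missing control. Adding control clinics would help attribution but would not raise the share of treated patients in a clinic's rate. Delivery mode, sample, data source and intended reading are all fixed in the protocol, so the point does not depend on what an analysis plan may add.

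**Working it through.** **The plan's own figure.** Section 9.2 gives 80.0% power for n = 200, effect size 0.20, two-sided 0.05, paired t-test. The noncentrality is 0.20 × √200 = 2.83, and the noncentral t gives 80.4%, so the figure reproduces. It covers the knowledge and intention scores only. No power or expected change is stated for clinic or system rates.

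**Inputs from the protocol.**
- Participants: 400 planned (1.1, 4.3, 8.1), at most 1000 (1.1).
- Clinics: 12, counted from the list in 5.1.
- Age groups: 2 (1.1).
- Quarters: "Study Duration: 36 months" gives 36/3 = 12 at most, if enrolment runs throughout.

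**Assumptions.**
- Participants are spread evenly over clinics and age groups.
- Baseline coverage is 48%, the statewide adolescent completion figure for 2016 in 2.2. Clinic baselines are not given.
- Eligible patients per clinic and age group, D, are not given. The range taken is 100 to 5000.

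**Step 1: participants per cell.**
- At 400: 400/12 = 33.3 per clinic; 33.3/2 = 16.7 per clinic and age group by the end; 16.7/12 = 1.4 new participants per quarter.
- At 1000: 83.3, 41.7 and 3.5.

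**Step 2: how far a single clinic's rate can move.** Shift = participants × uplift / D. The table takes the most favourable uplift: every participant is vaccinated and none would have been otherwise. The detectable difference is the before/after change from 48% that has 80% power (two-sided 0.05, equal denominators, two independent proportions).

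| D | Shift at 400 (points) | Detectable (points) | Power at 400 | Shift at 1000 (points) | Power at 1000 |
|---|---|---|---|---|---|
| 100 | 16.7 | 19.5 | 66% | 41.7 | about 100% |
| 250 | 6.7 | 12.5 | 32% | 16.7 | 97% |
| 500 | 3.3 | 8.8 | 18% | 8.3 | 75% |
| 1000 | 1.7 | 6.3 | 11% | 4.2 | 46% |
| 5000 | 0.3 | 2.8 | 5% | 0.8 | 13% |

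With 400 evenly spread, no row reaches 80% power even at full uplift. With a 50-point uplift, the most favourable row (D = 100) falls to 8.3 points and 22% power. The shift from one quarter's new participants is at most 16.7/12 = 1.4 points (D = 100), and 0.3 or less from D = 500 upward.

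**Step 3: how little background movement matches the effect.** At D = 500, 16.7 patients are participants and 483.3 are not. A change of 16.7/483.3 = 3.4 points among non-participants moves the clinic rate as much as vaccinating every participant.

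**Step 4: the pooled system rate.** All 400 count here. With an assumed 500, 1000 or 3000 eligible patients per clinic (both age groups together), the system has 6000, 12000 or 36000.
- Largest shift: 400/6000 = 6.7, 400/12000 = 3.3 and 400/36000 = 1.1 points.
- Detectable differences: about 2.6, 1.8 and 1.0 points.
- With a 50-point uplift, power is 98% at 5000 eligible patients, 81% at 10000, 52% at 20000 and 24% at 50000.

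**The case against.** The strongest reply is that no clinic denominator appears in the protocol, so the dilution is not established as a fact. That stands, and it limits the wording to very unlikely. At 1000 participants with full uplift, clinics with 250 patients per age group would show the change. Even spread is also doubtful. Five of the 12 clinics are named as adult or women's care, so adolescents may be concentrated in the other seven. If half of the 400 came from there, 200/7 = 28.6 per clinic: 28.6 points at D = 100, above the detectable 19.5, but 11.4 points at D = 250, still below 12.5. A parent may also bring more than one eligible child.

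A second reply is that dilution is not bias. In a pragmatic study, population impact is reach times effect, and a small clinic change is a valid answer about a low-reach programme. This stands too: the problem is low sensitivity together with attribution, not invalidity of the rate itself.

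Third, the clinic-level endpoints are tertiary/exploratory, 9.4.1 names no test of clinic rates, and participants' own doses are tracked separately. So a participant effect is not lost to the study as a whole.

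Three stronger readings are tempting:
- A reader might infer that dilution also hides the effect at system level. Step 4 does not support this. There the obstacle is the absence of a control.
- A reader might take 1.4 participants per cell as the content of a quarterly rate. That counts new enrolees only; about 17 accumulate per clinic and age group.
- A reader might conclude that the objective can never be answered by this measure. Without denominators the documents do not prove that.

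**Conclusion.** The mismatch between individual delivery and whole-clinic measurement is real. At the planned 400, about 33 participants per clinic and about 17 per clinic and age group are very unlikely to move a single clinic's rate detectably, unless clinics are small or enrolment nears 1000. Movement in that rate will mainly reflect patients outside the study. A pooled system rate could show a large uplift despite dilution, but with one group and state rates as the only outside comparison, neither a before/after change nor a gap from the state could be attributed to the intervention.

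The conclusion rests on even spread, a 48% baseline, the assumed range of D, and before and after rates treated as independent samples. If largely the same patients are counted both times, the detectable differences would be smaller, but the participants' share of each clinic would not change. Patient-level uptake is unaffected.

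**What to change.** In 4.1 and 8.1:
- Use the participant dose records already tracked to split each clinic's quarterly dose counts and denominators into enrolled participants and all other eligible patients.
- Report the non-participant rate as concurrent background beside the participants' uptake, and state that the comparison is descriptive because participants volunteer.
- Report the number and share of each clinic's doses given to participants as programme reach. It is not an impact measure, since it credits the intervention with doses that participants would have received anyway.
- Present changes in overall clinic and system rates as context, not as the effect of the intervention.

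The cost is one extra breakdown of clinic reports and record data that are already obtained, and a more modest clinic-level claim. It is best settled before the clinic reports are requested.

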8.2 STUDY SCHEDULE

8.2.2 ENROLLMENT/BASELINE

Enrollment will occur at the educational sessions to be hosted by CHE's to eligible DHHA patients.

8.2.3 INTERVENTION VISITS

Participants who indicate that either their adolescent children or they have not completed the HPV vaccine series at baseline, they will be refer to the PN intervention to schedule the needed HPV vaccine dose. Participants whose children or them missed the HPV vaccine dose appointment will receive a recall text or phone call to reschedule another vaccine appointment.

8.2.4 FOLLOW-UP VISITS

If participants indicate that their children or they have not completed the HPV vaccine series at 3-months and 6-months, they will be schedule for the HPV vaccine dose needed, and if they missed receiving it, they will be followed through a recall text or call to reschedule to receive the missed dose.

8.2.5 EARLY TERMINATION VISIT

If participants who receive the CHE education intervention indicate that their children or they have completed all the HPV vaccine doses recommended for them, they be terminated from receiving the PN intervention. Participants who are referred to the PN intervention to receive a needed HPV vaccine dose, will be terminated for further PN intervention if they complete the HPV vaccine series at the 3-month or 6-month follow-up period.

8.2.6 SCHEDULE OF EVENTS TABLE

HPV Educational Intervention and Data Collection	Baseline/ Intervention			Recall upon missed dose	Quarterly
Informed Consent	X				
Post-education (baseline survey)	X				
Gift card compensation	X				
PN vaccine referral/navigation	X			X	
PN vaccine follow-up/navigation				X	X
Clinic Assessment of HPV vaccination rates EMR system					X

8.3 ADVERSE EVENTS AND SERIOUS ADVERSE EVENTS

8.3.1 DEFINITION OF ADVERSE EVENTS (AE)

NA

8.3.2 DEFINITION OF SERIOUS ADVERSE EVENTS (SAE)

NA

8.3.3 CLASSIFICATION OF AN ADVERSE EVENT

8.3.3.1 SEVERITY OF EVENT

NA

8.3.3.2 RELATIONSHIP TO STUDY INTERVENTION

NA 8.3.3.3 EXPECTEDNESS

NA

8.3.4 TIME PERIOD AND FREQUENCY FOR EVENT ASSESSMENT AND FOLLOW-UP

NA

8.3.6 SERIOUS ADVERSE EVENT REPORTING

NA

8.4 UNANTICIPATED PROBLEMS

8.4.1 DEFINITION OF UNANTICIPATED PROBLEMS (UAP)

NA

8.4.2 REPORTING OF UNANTICIPATED PROBLEMS

NA

9 STATISTICAL CONSIDERATIONS

9.2 SAMPLE SIZE DETERMINATION

A sample size of 200 participants achieves 80.0% power to reject the null hypothesis of zero effect size (i.e., improvement in, HPV and HPV vaccine knowledge, and HPV vaccine intentions' scores) when the Cohen's effect size is 0.20 (small effect size)³⁴ and the significance level is 0.050 using a two-sided one sample paired t-test.

9.3 POPULATION FOR ANALYSES

The population for analyses will constitute all patients at DHHA who are parents of adolescents aged 9 to 17 years old who are eligible for the HPV vaccine series, as well as young adults ages 18 to 26 years old who are also eligible for the HPV vaccine series.

9.4 STATISTICAL ANALYSES

9.4.1 GENERAL APPROACH

The effects of the education intervention on the primary outcomes measured by the continuous scales regarding, HPV and HPV vaccine knowledge, and HPV vaccine intentions, will be assessed using two-sided one-sample paired t-test for the null hypothesis that the paired difference is 0 against the alternative hypothesis that the paired difference is not 0. Appropriate transformation and/or the non-parametric Wilcoxon test will be performed if the data suggests severe non-normality. The significant level is 0.05.

Exploratory analysis of the characteristics that influence participants' adherence (0=non-adherent; 1=adherent) to the recommended HPV vaccine dosage will be conducted use logistic regression analysis. Our analyses will adjust for co-variates that likely influence the primary outcomes and exploratory outcomes, which include prior HPV vaccine dosage. We will also adjust for other potential co-variates if our descriptive analysis suggests this may be needed. Summary descriptive statistics will be calculated and presented for all primary, exploratory outcomes for all participants, and for subgroups defined by participants predisposing (e.g., gender, age), enabling (e.g., insurance, barriers), and need (e.g., cancer risks) characteristics. The demographic characteristics of the participants will be presented with descriptive statistics also. The means, medians and the 95% confidence intervals will be calculated for continuous variables; the frequencies, estimated rates, and the exact 95% confidence intervals will be calculated for the binary and categorical variables.

10 SUPPORTING DOCUMENTATION AND OPERATIONAL CONSIDERATIONS

10.1 REGULATORY, ETHICAL, AND STUDY OVERSIGHT CONSIDERATIONS

10.1.1 INFORMED CONSENT PROCESS

10.1.1.1 CONSENT/ASSENT AND OTHER INFORMATIONAL DOCUMENTS PROVIDED TO PARTICIPANTS

Consent form describing in detail the study procedures, and risks are provided to the participant. Completion of the informed consent process is required prior to starting intervention/administering study product.

10.1.1.2 CONSENT PROCEDURES AND DOCUMENTATION

Informed consent process will be initiated prior to the individual's agreeing to participate in the study and continues throughout the individual's study participation. Extensive discussion of risks and possible benefits of participation will be provided to the participants and their families.

Consent forms will be IRB-approved, and the participant will be asked to read and review the document. The consent process will occur over the phone. All participants will receive a verbal explanation in terms suited to their comprehension of the purposes, procedures, and potential risks of the study and of their rights as research participants. Consent will be reviewed prior to participants receiving in any of the educational materials and before completing the surveys. The consent form will be read, and clarification will be confirmed, and questions will be addressed as needed. Participants will have time to review the consent prior to deciding if they would like to participate and will verbally acknowledge understanding and willingness to participate in the study prior to any procedure being done specifically for the study. We are unable to hold in person meetings due to COVID-19 restrictions. At this point in time those restrictions will remain indefinitely. Hosting virtual education sessions requires a high level of computer and technological literacy that has become a barrier to enrollment. Similarly, asking patients to complete a consent form that requires a digital e-signature and join a zoom call is too cumbersome and creates a barrier to enrollment. Thus, we will use a postcard consent that will be sent via text or email or will otherwise be made available to the subject in advance of the informed consent discussion. The participants may withdraw consent at any time throughout the course of the trial. The rights and welfare of the participants will be protected by emphasizing to them that the quality of their medical care will not be adversely affected if they decline to participate in this study.

The study allows the inclusion of non-English speaking and non-reading participants. Witnesses to these consent processes will be individuals not associated with the trial and will not have a conflict of interest.

10.1.3 CONFIDENTIALITY AND PRIVACY

Participant confidentiality is strictly held in trust by the participating investigators, their staff, and the sponsor-investigator(s) and their agents. This confidentiality is extended to cover the clinical information relating to participants. Therefore, the study protocol, documentation, data, and all other information generated will be held in strict confidence. No information concerning the study, or the data will be released to any unauthorized third party without prior written approval of the sponsor.

The study monitor, other authorized representatives of the sponsor-investigator, or representatives of the IRB may inspect all documents and records required to be maintained by the investigator, including but not limited to, medical records (office, clinic, or hospital) for the participants in this study. The clinical study site will permit access to such records.

The study participant's contact information will be securely stored at each clinical site for internal use during the study. At the end of the study, all records will continue to be kept in a secure location for as long a period as dictated by local IRB and Institutional regulations.

Study participant research data, which is for purposes of statistical analysis and scientific reporting, will be transmitted to and stored at the University of Colorado Cancer Center. This will not include the participant's contact or identifying information. Rather, individual participants and their research data will be identified by a unique study identification number. The study data entry and study management systems used by clinical sites and by the University of Colorado Cancer Center, research staff will be secured, and password protected. At the end of the study, all study databases will be de-identified and archived at the University of Colorado Cancer Center.

